To identify individual genes whose expression levels at pre-treatment are associated with pCR, we will apply two-sample *t* tests to compare responders and non-responders. Adjusted P values controlling for false discovery rate (Benjamini and Hochberg method) will be derived. In addition, to assess association of pre-specified immune gene signature with response, the median expression level of the component genes will be used to represent the signature and two-sample *t* tests will be used. For genes or signatures that emerge as significantly associated with response, logistic regression models will be used to assess their independent association with response after adjusting for known clinical prognostic factors. To identify pharmacodynamic markers, paired *t*-test will be carried out to examine immune gene expression differences between pre-treatment and post treatment samples. Additionally, association of gene expression levels after epigenetic priming with long term efficacy outcomes, such as PFS and DFS, will be explored using the Cox proportional hazards regression model. Hierarchical clustering superimposed with response status, relevant baseline or prognostic characteristics or

experimental factors will be performed using Spearman correlation and complete linkage to visualize the discriminating power of the immune gene expression and the correlative structure among the genes and the samples.

T cell receptor (TCR) deep sequencing

The change in tumor-infiltrating TCR between pre-treatment and post-epigenetic priming will be assessed by calculating the number of unique clonotypes comprising the top 25th percentile of cumulative reads after sorting by clone abundance. Repertoire change between sequencing experiments will be measured using Morisita's distance. This analysis will also be performed in subjects receiving adjuvant chemotherapy using the same statistical techniques to evaluate the impact of adjuvant MPDL3280A on circulating T cell repertoire remodeling.

Genomic signatures of response

It is hypothesized that tumors with highly mutated or copy-aberrant genomes will either overexpress native proteins or express novel mutant proteins, both of which may be recognized by the immune system and serve as tumor-specific antigens. Therefore the effect of genomic mutations on the immune landscape will be investigated in each of the cohorts in this study as follows.

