Tumor DNA will be isolated from pre-treatment tissue and from post-epigenetic priming specimens, and will be analyzed for copy number using the Human Genome CGH 244K Microarray (Agilent, Santa Clara, CA) and/or by next-generation sequencing. Results will be analyzed with DNA Analytics software (Agilent) and with the assistance of the UCSF Genome Core and the UCSF Biostatistics core. For copy number paired Wilcoxon signed-rank test will be applied to test difference of tumor gene copy number between pre and post treatment. Two-sample Wilcoxon signed-rank test will be used to test the gene copy number between tumor responders and non-responders for pre-treatment, post-treatment and changes before and after the treatment, separately. Multiple testing adjustment will be done by controlling false positive rate. Next-generation sequencing will take place using appropriate methods and biostatistical analyses. Annotation will be based on NCBI and UCSC databases. Chi-square test will be applied to obtain the significant variants associated with the clinical response.

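### The exploratory copy-number and variant analysis names a signed-rank test for independent groups, an error target that is literally per-test, and no stated adjustment for the variant screen

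*Combined protocol and SAP*

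**What the plan says.** All of this sits under 8.3.4, which covers exploratory endpoints.

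- **Platform.** In 8.3.4.1, Genomic signatures of response, tumor DNA is "analyzed for copy number using the Human Genome CGH 244K Microarray (Agilent, Santa Clara, CA) and/or by next-generation sequencing". The number of tests is not given.
- **Paired contrast.** "For copy number paired Wilcoxon signed-rank test will be applied to test difference of tumor gene copy number between pre and post treatment".
- **Responder contrasts.** "Two-sample Wilcoxon signed-rank test will be used to test the gene copy number between tumor responders and non-responders", and this is done "for pre-treatment, post-treatment and changes before and after the treatment, separately". That makes three responder families and, with the paired one, four in all.
- **Multiplicity.** "Multiple testing adjustment will be done by controlling false positive rate". No level, procedure or family is stated.
- **Variants.** After that sentence, sequencing methods are left open, and then: "Chi-square test will be applied to obtain the significant variants associated with the clinical response". No level, number of variants or adjustment is given.

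Two neighbouring analyses are specified differently. For mRNA signatures in 8.3.4.1, "Adjusted P values controlling for false discovery rate (Benjamini and Hochberg method) will be derived". For circulating antibodies, 8.3.4.2 compares clinical responders with nonresponders by a two-sided Wilcoxon rank-sum test. The mRNA text also sets out to find "individual genes whose expression levels at pre-treatment are associated with pCR", and it gives DFS alongside PFS as a long-term outcome.

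**The concern.** Three rules in one paragraph would mislead an analyst who followed them as written.

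First, responders and non-responders are different patients. A signed-rank test needs pairs or a single sample, so it cannot be applied to this contrast.

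Second, the false positive rate in its ordinary sense is the error rate of a single test. Holding it at a fixed level is what an unadjusted analysis already does. The false discovery rate and the family-wise rate are different targets, and the plan picks one of them for expression but not for copy number.

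Third, the variant screen comes after the adjustment sentence and has none of its own. Its chi-square test would be run on at most 29 patients per arm, where rare variants leave near-empty cells.

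At stake is how far a reported list of genomic features associated with response can be trusted. Separately, pCR and DFS are not among the endpoints in 2.4, and the trial enrols stage IV disease (3.3.1), so the mRNA wording does not match what the trial measures.

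**Working it through.** The genomic paragraph states no sample size, level, number of tests or error count, so it has no figure to reproduce. Every level and test count below is an assumption.

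**Group sizes.** Section 8.2 gives 29 patients per arm if both stages are completed. Continuing above 1 of 10 and rejecting above 5 of 29 gives alpha 0.04709 and power 0.8051, which match the stated 0.0471 and 80.5%. So 6 responders is the smallest count that rejects. The planned 30% gives 0.30 × 29 = 8.7, about 9. I therefore use 6 to 9 responders of 29; patients with usable tissue may be fewer.

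**Expected false hits per copy-number family** = number of tests × per-test level, with all nulls true:

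| Per-test level | 20,000 genes | 244,000 features |
|---|---|---|
| 0.05 | 1,000 | 12,200 |
| 0.01 | 200 | 2,440 |
| 0.001 | 20 | 244 |

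Multiply by 3 for the responder contrasts, or by 4 with the paired family. The 244,000 is read from the array's name; the 20,000 assumes one test per gene. The rank-sum test is discrete, which changes little: its exact size at nominal 0.05 is 0.0491 for 9 versus 20, or about 11,980 of 244,000. Correlation between neighbouring features leaves the expected count unchanged but makes the actual count much more variable. An arm stopped at stage 1 has at most 1 responder of 10; the smallest two-sided rank-sum p-value is then 2/10 = 0.20, and nothing can be declared at 0.05.

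**Under Benjamini-Hochberg** at an assumed q = 0.05, 9 versus 20, all nulls true and independent tests (200 simulated families), mean false hits were about 0.05 for 20,000 tests and 0.03 for 244,000.

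**Variant screen.** At 0.05 unadjusted, 100 variants give 5 expected false hits, 1,000 give 50, and 20,000 give 1,000. The number to be tested is not stated.

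**Exact size of the variant test** at nominal 5%, from binomial enumeration, at variant frequencies of 5% and 10%:

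| Responders vs non-responders | Chi-square, uncorrected | Fisher's exact |
|---|---|---|
| 6 vs 23 | 9.4%, 7.5% | 1.1%, 1.9% |
| 7 vs 22 | 1.7%, 2.9% | 0.3%, 1.0% |
| 8 vs 21 | 2.2%, 3.3% | 0.2%, 0.7% |
| 9 vs 20 | 2.9%, 4.5% | 0.3%, 0.9% |

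The jump at 6 versus 23 has a simple cause. If one patient carries the variant and is a responder, chi-square = 29 × n2 / (n1 × 28), where n1 and n2 are the numbers of responders and non-responders. For 6 versus 23 this is 667/168 = 3.97, above the 5% critical value of 3.84. For 7 versus 22 it is 638/196 = 3.26, below it. One carrier is enough for significance in the first case and not in the second.

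**The case against.** The strongest defence is that the sentence promises a multiple testing adjustment. With Benjamini-Hochberg named for expression in the same section, false positive rate may well be a slip for false discovery rate. That stands. A reader might infer that the plan as written would produce thousands of false hits; the documents do not support this. It needs the literal per-test reading, a level near 0.05 (or 0.01 on all 244,000 features), and enough tests. The plan states no level, the array is an and/or alternative to sequencing, and the tested quantity is gene copy number, not the probe.

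The signed-rank label also looks like a naming slip. It is called two-sample, the previous sentence handles the paired data separately, and 8.3.4.2 names rank-sum for the same kind of contrast. It would probably be noticed at analysis, and it generates no false hits itself. It is still wrong as written.

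A reader might also infer that chi-square inflates error here in general. It does not: among the splits checked, size exceeds 5% at these frequencies only at 6 versus 23. With a continuity correction, which the plan does not rule out, that split gives 1.1% and 1.4%. What stands is that the uncorrected test's size is erratic.

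Finally, it would be wrong to say that the genomic analysis refers to an outcome the trial lacks. The genomic paragraph refers to tumor responders and clinical response, which the trial measures. pCR and DFS are stray terms in the mRNA text only. The pCR sentence itself goes on to compare responders with non-responders, and DFS stands beside PFS, which is an endpoint.

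**Conclusion.** The point holds as a defect of specification in an exploratory analysis. The responder contrasts name a test that does not apply to independent groups. The multiplicity rule names a literally per-test rate without a procedure or level. The variant screen has no stated adjustment.

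The size depends on the reading. Literal use at an assumed 0.05 with all nulls true gives about 1,000 to 12,200 expected false hits per copy-number family. Reading the phrase as false discovery rate, with Benjamini-Hochberg at q = 0.05, gives fewer than 0.1. An analyst should not have to choose between readings that far apart after seeing the data.

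For variants, uncorrected chi-square size runs from about 1.7% to 9.4% across 6 to 9 responders of 29 at 5% to 10% variant frequency. No primary or secondary conclusion is affected, so this is a worthwhile correction of low priority.

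**What to change.** In 8.3.4.1, Genomic signatures of response:

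- Use the Wilcoxon rank-sum test for the three responder contrasts, and keep signed-rank for pre versus post only.
- Replace false positive rate with false discovery rate by Benjamini-Hochberg at a stated q. Define the families, for example each of the four copy-number comparisons and the variant screen, by cohort. State whether the unit is the gene or the array feature.
- Extend the same control to the variant tests, and use Fisher's exact test there.

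In the mRNA text, replace pCR with the trial's 24-week response and DFS with OS.

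This is SAP wording; it needs no new data and uses methods mostly already in the plan. The cost is sensitivity. There will be fewer nominal hits, and Fisher's test is conservative (about 0.2% to 1.9% in the cases above). With 6 versus 23, the smallest possible rank-sum p-value is about 4.21 × 10⁻⁶. Benjamini-Hochberg at 0.05 over 244,000 features would then need at least 4.21 × 10⁻⁶ × 244,000 / 0.05 = 20.5, so 21, features at that extreme before declaring any. Testing by gene (20,000) lowers this to 4.21 × 10⁻⁶ × 20,000 / 0.05 = 1.7, so 2, which is a reason to settle the unit of analysis in advance.

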8.3.4.2 Immune endpoints

Immune cell activation

For each arm individually, flow cytometry of circulating immune cell subsets will also be performed on pre-treatment blood and again after 9 weeks on vorinostat (post epigenetic priming). Established flow cytometry panels will examine T cell activation. Immune cell quantification will be summarized by changes from baseline to after treatment using descriptive statistics. Furthermore, paired Wilcoxon signed-rank test will be applied to test the pre-post treatment changes. When available, immune cells digested from resected tumor tissues will also be assessed by flow cytometry.

Circulating antibody detection and characterization

Spotted antigen arrays will be used to detect circulating antibodies will be performed on sera derived from the pretreatment and after 9 weeks on vorinostat. . After standard preprocessing of the protein array data, Cluster and Treeview software will be used for unsupervised clustering of the data with Pearson correlation and complete linkage. For each array, an antigen is identified as being detected if its value is above the median. To determine the number of up- and downmodulated antibodies, the difference in log₂ intensity values of pretreatment and post-treatment samples will be taken for each patient to identify antigens that are detected

differentially due to treatment. Number of antibodies with at least 2- or 4-fold difference between pretreatment and post-treatment samples will be compared between clinical responders and nonresponders by performing two-sided Wilcoxon rank sum test.

All correlative studies and assays will be performed in the [name] lab, in conjunction with Merck, with the help of [name] and other experts in the field.

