1.3 Rationale for the Proposed Study

1.3.1 Rationale for Epigenetic Immune Priming (EIP):

Clinically, epigenetic immune regulation has been implicated in priming lung cancer cells to PD-1 inhibitors which resulted in prolonged responses^{3,4}. The efficacy of PD-1 inhibitors has not been established; however the expression of PD-L1 in ER+ breast cancer is low. PD-L1

expression however has been shown to be a poor predictor of survival and PD-L1 expression has been suggested to increase as ER+ tumors become resistant to therapy.

The role of epigenetic modulation has been studied extensively in breast cancer therapy. Several investigators have shown that HDAC inhibitors have immune modulatory functions, including modulation of Tregs, FoxP3 expression, changes in TIL expression, induction of PD-L1 expression and blockage of PD-1. We have previously shown that epigenetic modulation with an HDAC inhibitor can reverse hormone therapy resistance and force cells into programmed cell death¹. Based on these preclinical studies, we had proposed two clinical trials testing HDAC inhibitors with hormonal therapy in ER+ breast cancer.

We hypothesize that pre-exposure of breast cancer cells to the HDAC inhibitor vorinostat (i.e., Arm A, sequential treatment) will result in down regulation of T-regulatory cells (Tregs) and FoxP3, which will increase the efficacy of PD-1 inhibitors, as measured by ORR, and prime cells to increased immune response. We therefore anticipate the schedule of administration may play an important role in the administration of this combination strategy.

Recent preclinical studies have further suggested that epigenetic priming may be even more effective in ER-negative tumors that do not respond to Immune check point inhibitors or have low PD-1/PD-L1 expression. The goal of this study is to demonstrate that Vorinostat can increase PD-1 and PD-L1 expression.

1.3.1.1 Prior studies with vorinostat in breast cancer:

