3.6 Randomization Procedures

This is an open-label randomized trial; therefore, the Sponsor, investigator and subject will know the treatment administered. Two arms will be tested, with each independent assessment. Patients will be randomized to either arm using a computerized randomization program by [name]. Patients will be further stratified by prior number of chemo- and hormonal therapies.

No randomization is required for ER-negative patients (patients must have biopsiable disease)

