8.3.4 Analyses of Exploratory Endpoints

8.3.4.1 Tissue based endpoints

Note: Tissue will be used for multiple different exploratory assays. In the event that there is insufficient tissue to perform all assays for an individual subject, the tissue should be prioritized for assays as follows, in which the first assay described is the highest priority.

Tumor PD-L1 assessment

PD-L1 protein expression on tumor tissue from pre-treatment and post-Cycle-3 biopsies, and any other tumor biospecimens obtained, will be evaluated immunohistochemically and scored on a scale of 0, 1, 2, or 3. This scoring will be used for the determination of relationships between tumor PD-L1 expression and clinical responses described above. Specifically, in addition to hypothesizing that delayed pembrolizumab treatment (i.e., Arm A) will increase tumor response, we hypothesize that (i) PD-L1 expression will stimulate tumor response, (ii) but will not be associated with treatment (because PD-L1 is stimulated by vorinostat not pembrolizumab).

For analysis, PD-L1 expression level, scored as {0,1,2,3}, will be classified as binary (0 =negative; 1-3 =positive); across two time-points, this defines four types of PD-L1 participants: {0,0; 0,1; 1,0; 1,1}. We will use logistic regression to estimate Cycle-6 tumor response rate (95% CI) as a function of study arm and PD-L1 level at baseline and Cycle 3. Either time-point will be eliminated from the model if its effect is weak ($p>0.2$), leaving two types of PD-L1 participants: either {0,0; 1,1} or {0,0; 0,1}.

Tissue immune subset quantification and localization

For all subjects, immune cell subsets and localization will be summarized by changes from baseline to after treatment using descriptive statistics.

Immune cell mRNA signatures of response

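### No immune readout is compared between the two randomised ER+ arms, so a within-arm change in circulating immune cells cannot be attributed to schedule

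*Combined protocol and SAP*

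**What the plan says.** Section 8.3.4.2 (Immune cell activation) covers circulating subsets: "For each arm individually, flow cytometry of circulating immune cell subsets will also be performed on pre-treatment blood", with a second sample after 9 weeks on vorinostat. Changes are summarised descriptively and then tested: "paired Wilcoxon signed-rank test will be applied to test the pre-post treatment changes". On content it says "Established flow cytometry panels will examine T cell activation". Neither Tregs nor FoxP3 is named anywhere in section 8.3.4.

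The other immune readouts in section 8.3.4 are handled as follows:
- Tissue immune subsets: "For all subjects, immune cell subsets and localization will be summarized by changes from baseline to after treatment using descriptive statistics". There is no test and no split by arm.
- Immune gene expression: paired pre-post t-tests, or responders against non-responders.
- T-cell receptor sequencing: change from before treatment to after priming.
- Antibody arrays: counts of changed antibodies "will be compared between clinical responders and nonresponders by performing two-sided Wilcoxon rank sum test".
- PD-L1: study arm enters a logistic model, but the outcome of that model is tumour response.

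On schedule, section 1.3.1 says pre-exposure to vorinostat, which it calls the sequential arm, "will result in down regulation of T-regulatory cells (Tregs) and FoxP3, which will increase the efficacy of PD-1 inhibitors". It then expects that the timing of administration may play an important role. Section 3.6 sets up the comparison for ER+ disease: "Patients will be randomized to either arm using a computerized randomization program". ER-negative patients (Arm C) are not randomised.

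**The concern.** The first primary objective is to find the best approach to priming. The trial randomises ER+ patients between two schedules, and the rationale links schedule to an immune mechanism. The randomised contrast is the only comparison in the trial that can isolate schedule's effect on the immune readouts, and the plan does not use it.

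A pre-post change within one arm combines schedule with everything else that happens over the period: vorinostat, tamoxifen, time on study and regression to the mean. A fall in a subset in the sequential arm is what one would also see if schedule made no difference.

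For flow cytometry there is a second risk. Two separate p-values, one per arm, invite comparison, and finding significance in one arm but not the other is not evidence that the arms differ.

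**Working it through.** **1. The plan's own figures.** Section 8 gives operating characteristics only for response. Per arm: 10 patients in stage 1, stop with 0 or 1 responses, 29 in total, 10% against 30%. The final cut-off is not stated. Taking rejection at 6 or more responses, the exact two-stage binomial sum gives alpha 0.0471 and power 0.805, so both stated figures reproduce. No effect size, SD, alpha or power is given for any immune endpoint, and everything below rests on assumed values.

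**2. How many pairs there may be.** The chance that an arm passes stage 1 is 1 - 0.736 = 0.264 at a 10% response rate and 1 - 0.149 = 0.851 at 30%. With independent arms, both reach 29 with probability 0.264² = 7% or 0.851² = 72%. Both 10 and 29 per arm therefore matter, before any loss of samples.

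**3. Discordance between two equal arms.** Let p be the power of the within-arm test (two-sided 0.05, assumed). With the same true change in both arms, exactly one is significant with probability 2p(1 - p):

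| Within-arm p | 2p(1 - p) |
|---|---|
| 0.05 (no change) | 9.5% |
| 0.20 or 0.80 | 32% |
| 0.30 or 0.70 | 42% |
| 0.50 | 50% |
| 0.90 | 18% |

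Simulating the paired Wilcoxon test (normal data, 4,000 trials per setting, common change in units of the SD of the change) gives:

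| Common change | 10 per arm | 29 per arm |
|---|---|---|
| 0 | 8% | 10% |
| 0.3 | 22% | 45% |
| 0.5 | 41% | 42% |
| 0.8 | 48% | 4% |
| 1.0 | 34% | 0.2% |

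A direct rank-sum test of the changes between the same equal arms is falsely significant in 4-6% of trials throughout.

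**4. What a direct comparison can show.** Assume a baseline-to-post correlation of 0.6 and count in SDs of a single measurement. ANCOVA leaves a residual SD of √(1 - 0.6²) = 0.8. For a true difference of 0.5 SD the standardised difference is 0.5/0.8 = 0.625. The noncentrality is 0.625 × √(n/2): 1.40 for n = 10 and 2.38 for n = 29. Simulated power is about 24% and 64%; the noncentral t gives 26% and 65%. At 0.8 SD, power is about 53% with 10 per arm and 96% with 29. The 95% CI half-width is about 2.11 × 0.8 × √(2/10) = 0.75 SD with 10 per arm and 2.00 × 0.8 × √(2/29) = 0.42 SD with 29.

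**5. Which time point carries schedule.** Under Table 5.1, one ER+ arm starts pembrolizumab in cycle 1 and the other in cycle 2. By the end of cycle 3 the arms have had three and two doses, so both are exposed. Section 6.2.4.4 and Table 6 also collect blood at cycle 1 day 10-12, when only one ER+ arm has started pembrolizumab. Section 8.3.4.2 does not analyse that sample.

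**The case against.** The strongest defence is that the analysis matches the stated objectives. The exploratory immune objectives in the synopsis and section 2.3 largely concern change from before to after therapy. Sections 3.6 and 8.0 say each arm is assessed independently. The schedule remark in 1.3.1 is hedged, and its consequence is to be measured by response rate. These endpoints are exploratory. All of this stands, and it limits the point to an improvement in an exploratory analysis. It does not remove the gap: independent assessment suits the per-arm response test, but it cannot answer a question about schedule.

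Four stronger readings are tempting and not supported.
- That all immune readouts are tested within each arm. Only flow cytometry is; the others are descriptive, pre-post with no arm split stated, or by response.
- That the Treg/FoxP3 hypothesis is wholly untested. A paired test could show a fall, if the panels measure these cells; it cannot say that schedule caused it.
- That the plan will read significance in one arm only as a schedule effect. No section proposes that inference.
- That equal arms will often look different whatever the truth. This holds for small to moderate changes, and not when nothing changes or when the change is large with 29 per arm.

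It is also fair that a direct comparison has little power at these sizes, and that a contrast at week 9 alone would be diluted because both arms are by then on pembrolizumab. The fix allows for both.

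**Conclusion.** The concern holds in limited form. Section 8.3.4 contains no between-arm analysis of any immune readout for the randomised ER+ arms, so the trial as planned cannot attribute an immune change to schedule. Comparing the two flow cytometry p-values would be a poor substitute. Equal arms would split in 32-50% of trials when within-arm power is 20-80%, about 10% with no change, and under 5% for changes of 0.8 SD or more with 29 per arm. These figures assume normal changes, independent arms, two-sided 0.05 tests and effect sizes that the documents do not give.

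The primary alpha, power and stopping rule are unaffected. The loss is confined to the mechanistic conclusion about schedule. It is worth correcting because the randomisation and the samples are already in the plan.

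**What to change.** In section 8.3.4, for Arms A and B only, add an exploratory baseline-adjusted between-arm difference with 95% CI (ANCOVA of the on-treatment value on the log or rank scale, with randomised arm and the patient's own baseline):
- circulating subsets at cycle 1 day 10-12 and at the end of cycle 3;
- tissue subsets at the end of cycle 3.

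Report Tregs/FoxP3 first where the panels measure them, and state whether they do. Present the results as estimates with intervals, not as tests. Say that within-arm p-values are descriptive and will not be compared across arms. Keep the non-randomised Arm C separate.

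Before the contrast is given a direction, reconcile which ER+ arm is sequential. Sections 1.3.1 and 3.1 give that label to Arm A. The synopsis gives it to Arm B. Table 5.1 and the Table 6 calendar show Arm A starting pembrolizumab in cycle 1 and Arm B in cycle 2, whereas the synopsis study design has Arm A starting in cycle 2.

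The cost is SAP wording and a few model fits, with no new patients or sampling times. If the current blood panels do not cover Tregs/FoxP3, that readout is left out of the blood analysis unless the sponsor chooses to add it.

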6.2.4.4 Logistics on Immune modulation

For immune assays we will collect 60cc of blood in green top tubes at baseline and day 10-12 in cycle 1 and on day 17-18 in cycle 3, at the time points specified above for tumor biopsies, FFPE for immune cell infiltrate and a frozen section will be obtained for TCR sequencing.

Exploratory Objectives

1. To define the treatment-induced effects on circulating immune cells.
2. To assess the presence of antigen-specific immune responses to a broad panel of candidate tumor antigens.

At the prespecified endpoints: we will obtain

- Immunohistochemistry and gene expression analysis for immune cell subset quantification and localization within tumors
- Flow cytometry to evaluate changes in intra-tumoral and circulating immune cells
- T cell receptor (TCR) deep sequencing of tissue samples from pre-treatment biopsies and post-treatment biopsies, and post-treatment circulating T cells.
- Immune response mRNA expression analysis to derive signatures associated with tumor response
- Identification of genomic mutations and gene copy aberrations associated with response and resistance to therapy
- Antigen array-base detection of circulating antibody responses

These assays will be obtained in conjunction with [name] lab.

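### Two exploratory immune analyses are wrong as written: the circulating TCR change names patients and a drug not in this trial and lacks a baseline sequence, and the antibody detection rule marks half of the antigens in every sample

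*Combined protocol and SAP*

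**What the plan says.** **Circulating TCR.** Section 6.2.4.4 lists TCR deep sequencing of "pre-treatment biopsies and post-treatment biopsies, and post-treatment circulating T cells". Tissue is sequenced at two time points and blood at one. Section 8.3.4.1 measures repertoire change between sequencing experiments by Morisita's distance. It then extends the analysis to people on adjuvant chemotherapy, with the aim "to evaluate the impact of adjuvant MPDL3280A on circulating T cell repertoire remodeling".

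**Antibody arrays.** The second exploratory objective in 6.2.4.4 is "To assess the presence of antigen-specific immune responses to a broad panel of candidate tumor antigens". Section 8.3.4.2 runs antigen arrays on "sera derived from the pretreatment and after 9 weeks on vorinostat". The detection rule is "For each array, an antigen is identified as being detected if its value is above the median". A separate step takes each patient's pre/post difference in log2 intensity: "To determine the number of up- and downmodulated antibodies". The test follows: "Number of antibodies with at least 2- or 4-fold difference between pretreatment and post-treatment samples will be compared between clinical responders and nonresponders", by a two-sided Wilcoxon rank sum test.

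**Outcome terms.** In 8.3.4.1, individual genes are screened for whether their "expression levels at pre-treatment are associated with pCR", by comparing responders with non-responders. The long-term outcomes given as examples are PFS and DFS.

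**The concern.** A stated rule should give an informative result when it is followed literally. Two of these do not.

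The circulating TCR sentence appears to be carried over from another protocol. Followed as written, it selects nobody, and the sequencing list does not supply the pre-treatment blood sequence that a change measure needs.

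The antibody rule fixes the number detected by arithmetic. Whether antigen-specific responses are present is a question of detection, and this is the only detection rule in the plan. A call that marks the same share of antigens in every sample cannot answer it.

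Immune priming is the rationale of the trial, so these readouts will be used to interpret it even though they are exploratory. If the rules are repaired only after the data are seen, the population, the cut-off and the responder definition can all be chosen to suit the result.

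**Working it through.** The plan gives no sample size, power or expected value for these readouts, so there is no stated figure to reproduce. The TCR part is checked by comparing sections, the array part by arithmetic and a small simulation.

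**1. Circulating TCR: who is eligible?**
- 3.3.1: patients have stage IV disease.
- Table 5.1: vorinostat and pembrolizumab in all arms, plus tamoxifen in Arms A and B.
- 6.3.3: chemotherapy and immunotherapy not specified in the protocol are prohibited during screening and treatment.
- 8.1: the only other mention of MPDL3280A, as a historical response rate (19%).

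No patient receives adjuvant chemotherapy or adjuvant MPDL3280A on study. Section 3.3.1 allows ER-negative patients to have had PD-1 or PD-L1 inhibitors before entry, but no study sample brackets that treatment.

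**2. Circulating TCR: which sequences exist?** Morisita's distance compares two repertoires.

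| Compartment | Pre-treatment sequence listed | Post-treatment sequence listed |
|---|---|---|
| Tumor | yes | yes |
| Circulating T cells | no | yes |

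The blood itself is available: 6.2.4.4 draws 60 cc for immune assays at baseline, on day 10-12 of cycle 1 and in cycle 3. Only the baseline entry in the sequencing list is missing.

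**3. The median rule.** For m distinct values on one array, the number above that array's own median is floor(m/2). For m = 100 this is 50, and for m = 101 it is also 50. Any order-preserving rescaling of the array leaves the number unchanged. Because the total is the same before and after treatment, antigens gained minus antigens lost is always 0.

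**4. Simulation.** The plan gives neither array size nor noise, so the inputs are illustrative: pre-treatment log2 intensity normal with mean 8 and SD 0.5, pre/post noise SD 0.3, and a true rise of 4 log2 units in 0%, 5% or 60% of antigens. For m = 1000:

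| True rise | Detected pre | Detected post | Gained / lost | At least 2-fold | At least 4-fold | At least 2-fold and detected at either time |
|---|---|---|---|---|---|---|
| 0% | 500 | 500 | 92 / 92 | 1 | 0 | 1 |
| 5% | 500 | 500 | 104 / 104 | 51 | 50 | 51 |
| 60% | 500 | 500 | 192 / 192 | 601 | 600 | 502 |

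The number detected does not move, even when 60% of antigens truly rise. With m = 5000 it was 2500 throughout. The fold-change count does follow the signal and does not need the detection call. Using detection as a filter can change that count (601 to 502 in the last row), and the plan does not say whether it is one.

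**5. Outcome terms.** The trial plans no surgery and defines neither pCR nor DFS as an endpoint. Response is classified by RECIST in 7.3. Section 8.3.2 counts stable disease or better at 24 weeks, and the PD-L1 model in 8.3.4.1 uses response at cycle 6. The responder groups used in 8.3.4 are therefore not tied to one definition.

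**The case against.** The other side has several good points, and each limits what can be claimed.

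- *A reader might infer that the antibody readout cannot be derived.* It can. The only antibody comparison planned is the 2- or 4-fold count by response, which comes from log2 differences and needs no detection call. Nor does the plan say that the number detected will be reported or tested, so it does not commit itself to answering the second objective with a fixed 50%. What stands is that the detection call is uninformative for that objective.
- *The reference set for the median is not named.* A median taken across arrays or from control spots would not force one half in every sample. The wording ties the rule to each array, so the array's own median is the natural reading, but the plan should say so.
- *A reader might want a false-detection rate, or blame the median rule for chance fold changes.* Both would need a true binding fraction or a noise level that the documents do not give. Chance fold changes would also occur without any median cut-off. No such percentage is claimed here.
- *A reader might infer that no baseline blood exists, or that the objective on circulating immune cells is lost.* Baseline blood is drawn, and 8.3.4.2 plans paired flow cytometry with a signed-rank test, which serves that objective. Only the circulating repertoire change lacks a workable plan.
- *A reader might infer that the gene analysis has no endpoint.* The pCR sentence itself compares responders with non-responders, and PFS stands beside DFS. These are mislabels, not an empty analysis.

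**Conclusion.** The point holds for two exploratory analyses. The circulating TCR change, as written, has no eligible patients and no baseline sequence. The tumor TCR change has both time points and stands. The antibody detection rule, assuming that the median is the array's own, marks half of the antigens in every sample and so says nothing about whether antigen-specific responses are present. The fold-change comparison remains computable. The pCR and DFS wording is a minor defect of the same kind.

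Nothing here touches the primary endpoint or the Simon design. The reason to act is that both rules fail when followed literally and the repair is cheap, most usefully made before samples are processed. The TCR finding rests on the text alone. The array finding rests on the own-array reading, and the simulated counts only illustrate it.

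**What to change.** 1. **Section 8.3.4.1, TCR.** Replace the adjuvant chemotherapy and MPDL3280A sentence with an analysis of circulating repertoire change in Arms A to C, baseline versus cycle 3. In 6.2.4.4, add baseline circulating T cells to the sequencing list, using the 60 cc already drawn. Cost: one more sequencing run per patient, with no extra blood.
2. **Section 8.3.4.2, arrays.** Define detection against negative-control spots on the same array, for example the control mean plus a pre-stated multiple of the control SD. State whether detection at either time point filters the 2- and 4-fold counts. This assumes that the arrays carry such spots, which the documents do not say. Cost: wording only, though fewer antigens may be called detected.
3. **Section 8.3.4.1, outcomes (minor).** Replace pCR with one pre-stated RECIST-based responder definition, used throughout 8.3.4, and say whether stable disease at 24 weeks counts. Replace DFS with OS, since PFS is already listed. Cost: wording only.
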